### 4.2. Disposition Information

The number of subjects in the following disposition categories will be summarized throughout the study using all treated analysis set:

- Subjects screening
- Subjects receiving study agent
- Subjects ongoing treatment

- Subjects completing the study
- Subjects who discontinued study agent
- Reasons for discontinuation of study agent
- Subjects who terminated study prematurely
- Reasons for termination of study
- Analysis Sets

Listings of subjects will be provided for the following categories:

- Subjects who discontinued study agent
- Subjects who terminated study prematurely

#### **4.3. Extent of Exposure**

Descriptive statistics (N, mean, SD, median, and range (minimum, maximum)) will be presented for the following parameters:

- Treatment duration
- Cumulative total dose
- Dose intensity
- Relative dose intensity
- Time on Study

Dose withholding (any dose skip with 7 days or more) and dose reduction will be summarized for the number of subjects with any dose withholding (at least one reported dose withholding), any dose reduction (at least one reported dose reduction), and any dose modification (at least one dose withholding or dose reduction), as well as the frequency and reason of dose withholding and dose reduction.

#### **4.4. Protocol Deviations**

In general, protocol violations/deviations will be reviewed by the study team during the study, and important protocol deviations will be determined based on the review. The information of important protocol deviations will be generated based on the review outcome for all subjects. Important protocol deviations will be summarized by center. A corresponding listing is also generated. COVID-19 related protocol deviations will be provided in a separate listing.

#### **4.5. Medical History**

Medical history collected at baseline or screening visit will be summarized by system-organ class and preferred term for all treated analysis set. Transplant history and underlying disease will be summarized and listed.

#### **4.6. Prior and Concomitant Medications**

Concomitant medications will be coded using the World Health Organization Drug Dictionary (WHO-DD). Prior medications are defined as any therapy used before the first dose of the study agent. Concomitant medications are defined as any therapy used on or after the same day as the first dose of study agent, including those that started before and continue on after the first dose of study agent.

Summaries of concomitant medications will be presented by therapeutic class and preferred term. In addition, summary of usage of CYP3A inhibitors as well CYP3A inducers will be provided separately. A list of common CYP3A inhibitors and inducers is provided in Attachment 1. The summary of usage of anticoagulants and antiplatelets will also be provided.

Prior and subsequent cGVHD therapies after the start of study drug will be summarized and listed separately. Concomitant use of additional immunosuppressants will be summarized and listed.

### **5. EFFICACY**

#### **5.1. Analysis Specifications**

##### **5.1.1. Level of Significance**

All tests will be 1-sided. The primary efficacy endpoint will be tested at the overall significance level of 0.025. For result presentation purpose, a 2-sided 95% confidence interval will be used.

##### **5.1.2. Data Handling Rules**

Unless specified otherwise, missing values will not be imputed and partial dates are described in Section 2.10.

#### **5.2. Primary Efficacy Endpoint(s)**

The overall response rate (ie, the proportion of responders [CR or PR]).

##### **5.2.1. Definition**

Response will be defined by the NIH Consensus Development Project Criteria (2014) and must occur:

- In the absence of new therapy for cGVHD
- In the absence of progression of the underlying disease that was the indication for transplant (or posttransplant lymphoproliferative disease [PTLD]), or death.

##### **5.2.2. Analysis Methods**

The all treated analysis set will be used for primary endpoint. The response evaluable analysis set will be used for sensitivity analysis.

The primary analysis for primary endpoint will be conducted at the time when the last subject has completed the efficacy assessment at Week 37 or has discontinued treatment before Week 37. Final analysis will be conducted at the study end.

The overall cGVHD response rate (CR + PR) and its 95% confidence interval will be calculated with the exact test for binomial distribution in the all treated population. The study is considered to be positive if the lower limit of the exact 2-sided 95% confidence interval based on binomial distribution exceeds the threshold value (0.25).

### 5.3. Major Secondary Endpoints

The secondary efficacy endpoints are:

- Rate of sustained response for at least 20 weeks
- Duration of response
- cGVHD response rate at each timepoint
- Corticosteroid requirement changes over time
- Change in symptom burden measured by the Lee cGVHD Symptom Scale

#### 5.3.1. Definition

##### Sustained Response:

Sustained response is defined as NIH-defined response that sustain continuously for at least 20 weeks (140 days). Considering 7 days at maximum visit window allowed by protocol, the bound of sustained response is defined as 133 days. Intermittent SD assessment between response assessments is allowed.

##### Duration of Response:

Duration of Response (DOR) is defined as the interval between the date of initial documentation of a response (CR or PR), and the date of first documented evidence of progressive disease, death, or date of censoring if applicable, for responders only. DOR will be right censored based on [Table 2](#) for all responders:

**Table 2: Date of Event or Censoring for Duration of Response**

Situation	Date of DOR Event or Censoring	Outcome
Death or disease progression occurred on or before the start date of subsequent cGVHD treatment documented at scheduled disease assessments or between two scheduled disease assessments.	Earliest date of adequate disease assessment documenting disease progression or date of death, whichever occurs first.	Event
New subsequent cGVHD treatment before disease progression	Date of last adequate disease assessment prior to or on start date of the new subsequent cGVHD treatment	Censored
Not known to have progressed or died at the data analysis cutoff date (this includes subjects who were known to have progressed or died after the data analysis cutoff date)	Date of last adequate disease assessment showing no evidence of disease progression.	Censored

For subjects who met more than one censoring condition, DOR will be censored according to the earliest censoring condition/date. For subjects who have incomplete date for initiation of subsequent cGVHD treatment, the partial date will be imputed as the earliest possible date that incorporates the available information from the partial date and does not contradict last dose date of study drug.

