9.2. Efficacy

9.2.1. Efficacy Evaluations

NIH Consensus Panel Criteria for Overall Response

Response will be defined using the NIH Consensus Panel Chronic GVHD Activity Assessment (2014) ([Attachment 4](#), [Attachment 5](#), and [Attachment 6](#)). Skin, mouth, liver, upper and lower GI, esophagus, lung, eye, and joint/fascia are the organs or sites considered in evaluating overall response.

- Complete Response (CR) is defined as resolution of all manifestations in each organ or site.
- Partial Response (PR) is defined as improvement in at least 1 organ or site without progression in any other organ or site.
- cGVHD Progression is defined as clinically meaningful worsening in one or more organs regardless of improvement in other organs. Note that mixed response (ie, improvement in at least 1 organ accompanied by progression in another organ) is considered cGVHD progression.
- Stable disease (SD): response that does not meet the criteria for CR, PR, or cGVHD progression.

Please refer to NIH Response Assessment Manual provided by the sponsor for further details.

Lee cGVHD Symptom Scale

All subjects in the study will complete the Lee cGVHD Symptom Scale ([Attachment 3](#)) at all response assessment visits.

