Score 1: Normal total bilirubin with ALT ≥3 to 5 x ULN or alkaline phosphatase ≥3 x ULN

Score 2: Elevated total bilirubin but ≤3 mg/dL or ALT >5 ULN

Score 3: Elevated total bilirubin >3 mg/dL

Overall Response:

Skin, mouth, liver, upper and lower GI, esophagus, lung, eye, and joint/fascia are the organs or sites considered in evaluating overall response.

- Complete Response (CR) is defined as resolution of all manifestations in each organ or site.
- Partial Response (PR) is defined as improvement in at least 1 organ or site without progression in any other organ or site.
- cGVHD Progression is defined as clinically meaningful worsening in one or more organs regardless of improvement in other organs. Mixed Response: CR or PR in at least 1 organ accompanied by progression in another organ is considered cGVHD progression.
- Stable disease (SD): response that do not meet the criteria for CR, PR, or cGVHD progression.

If a patient shows overall cGVHD improvement while organ responses indicate progression in one or more organs, cGVHD assessment should be repeated at a different timepoint, to confirm progression, before discontinuing study drug. If progression is confirmed, time to progression will be calculated using first date of cGVHD progression. Lack of Response includes categories of cGVHD progression or stable disease.

Reference:

Attachment 6: Chronic GVHD Activity Assessment – Patient Self Report**FORM B****CHRONIC GVHD ACTIVITY ASSESSMENT-PATIENT SELF REPORT**

Symptoms		Not Present As Bad As You Can Imagine										
Please rate how severe the following symptoms have been in the last seven days. Please fill in the circle below from 0 (symptom has not been present) to 10 (the symptom was as bad as you can imagine it could be) for each item.		0	1	2	3	4	5	6	7	8	9	10
Your skin itching at its WORST?												

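### The SAP's duration-of-response event omits the confirmation condition that protocol Attachment 5 sets for subjects who improve overall while an organ progresses

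*SAP*

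**What the plan says.** SAP 5.3.1 ends DOR at "the date of first documented evidence of progressive disease, death, or date of censoring if applicable, for responders only". Table 2 then fixes the event date as "Earliest date of adequate disease assessment documenting disease progression or date of death, whichever occurs first". Neither place mentions confirmation, and no other part of the SAP brings it in.

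Protocol 9.2.1 classes a mixed response as progression: "improvement in at least 1 organ accompanied by progression in another organ) is considered cGVHD progression". Attachment 5 repeats this and then singles out one situation: "If a patient shows overall cGVHD improvement while organ responses indicate progression in one or more organs". For that subject, "cGVHD assessment should be repeated at a different timepoint, to confirm progression, before discontinuing study drug". The next sentence is an analysis rule: "If progression is confirmed, time to progression will be calculated using first date of cGVHD progression". Protocol 9.1.3 also speaks of confirmed progression as the point at which study drug stops.

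Other protocol passages do not mention confirmation: the last sentence of 8.1.3 (subjects who meet progression criteria are treatment failures), the discontinuation list in 10.2, and the DOR endpoint in 2.1.

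For the 20-week endpoint, SAP 5.3.1 requires a continuous response with a working bound of 133 days, and makes one allowance: "Intermittent SD assessment between response assessments is allowed".

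**The concern.** Protocol 8.1.3 describes chronic GVHD as fluctuating and warns that closely spaced evaluations pick up temporary exacerbations. Attachment 5 allows for this when the subject is improving overall. If the SAP is programmed as written, a temporary organ worsening that the repeat does not bear out becomes a DOR event. A subject who is still responding is then recorded as having progressed.

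DOR and the sustained-response rate are the secondary endpoints that speak to durability. In an open-label, single-arm trial with about ten expected responders, a rule left open until responses are known could be settled either way, and one subject is visible in the result.

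**Working it through.** **1. The plan's own figure.** The documents state no figure for DOR. The nearest is the power for overall response: N = 17, true rate 60%, success if the exact 95% lower limit exceeds 25%. The smallest qualifying count is 9 of 17 (lower limit 0.278). Power is P(X ≥ 9 | 17, 0.60) = 0.801 and the one-sided type I error is P(X ≥ 9 | 17, 0.25) = 0.0124. The stated 80% is reproduced, and nothing below changes it.

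**2. The rules side by side, for a responder with overall improvement and organ progression at one assessment.**

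| Repeat assessment | Protocol Attachment 5 | SAP 5.3.1 and Table 2, read literally |
|---|---|---|
| Confirms progression | Progression, dated at the first assessment | Event, dated at the first assessment |
| Does not confirm | No progression date is calculated | Event, dated at the first assessment |
| Not done | Not stated | Event, dated at the first assessment |

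The documents part only in the second row.

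**3. Effect on one subject's DOR (assumed subjects, response continuing to Week 37).** Days = 7 × (difference in weeks).

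- Response at Week 5, unconfirmed progression at Week 13. SAP: 7 × 8 = 56 days, event. Attachment 5: 7 × 32 = 224 days, censored.
- Response at Week 13, unconfirmed progression at Week 25. SAP: 7 × 12 = 84 days, event. Attachment 5: 7 × 24 = 168 days, censored.

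**4. Effect on sustained response, if an unconfirmed progression breaks the run.** The bound is 133 days. The SAP does not say that the run must start at the first response.

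- First subject, back in response at a repeat at Week 15: the later run is 7 × (37 − 15) = 154 days, so the subject can still qualify.
- First subject, next documented response at Week 25: 7 × (37 − 25) = 84 days, not enough by Week 37.
- Second subject, back in response at Week 27: 84 days before and 7 × (37 − 27) = 70 days after, neither enough by Week 37. The unbroken run would be 168 days. If response lasts to Week 49, the later run is 7 × (49 − 27) = 154 days and qualifies.

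So the status may or may not change, depending on timing.

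**5. Size in the trial.** Expected responders: 0.60 × 17 = 10.2, about 10. One event among 10 at risk lowers the Kaplan-Meier curve by 1/10 = 10 points. One subject's change in sustained status moves that rate by 1/17 = 5.9 points.

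The probability q that a responder has an unconfirmed progression is not in the documents. Over an assumed range, with 10 responders:

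| q | Expected extra events, 10q | Chance of at least one, 1 − (1 − q)^10 |
|---|---|---|
| 5% | 0.5 | 40% |
| 10% | 1.0 | 65% |
| 20% | 2.0 | 89% |

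A hypothetical set of 10 responders has true events at days 84, 140 and 168 and seven subjects censored at day 224. Recode some of the seven as events at day 56. With none or one recoded, the median is not reached (the curve ends at 0.7 or 0.6). With two it is 168 days, and with three it is 140 days.

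**The case against.** The strongest reply is that the SAP follows the protocol's DOR endpoint, which does not mention confirmation, and that 8.1.3 and 10.2 do not mention it either. Confirmation appears only in 9.1.3 and in a conditional recommendation in Attachment 5 tied to stopping drug. This stands in part: the protocol has no uniform confirmation rule from which the SAP departs. But the Attachment 5 sentence that follows the recommendation is about calculating time to progression, so it is an analysis rule for the case it describes.

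A second reply is that Table 2 takes progression as already determined under the protocol and only says which date to use. The sponsor's NIH Response Assessment Manual, cited in 9.2.1 and not available here, may settle the matter. That is possible, but the SAP does not say so, and "the date of first documented evidence of progressive disease" points to the first assessment.

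A third is that DOR is descriptive, the sustained rate has no success threshold, and the literal rule shortens DOR, which is conservative for an efficacy claim. All of this is correct and limits the weight of the point.

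A reader might also infer more than the texts support. Table 2's earliest-date convention is not wrong in itself, since Attachment 5 uses the same date once progression is confirmed. Nor does every mixed response need confirmation: one organ better and one worse is progression under 9.2.1, and the repeat applies only where there is overall improvement as well.

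**Conclusion.** The gap is real but narrow. For a responder with overall improvement, organ progression and a repeat that does not confirm it, the SAP read literally records a DOR event that Attachment 5 would not count. Elsewhere the event dates agree, or Attachment 5 is silent because no repeat was done.

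Each such event costs about 10 points on the Kaplan-Meier curve. That assumes about 10 responders, all still at risk, and the difference closes if the subject truly progresses later. The number of such subjects is unknown and may be zero.

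A reader might infer that these subjects also fail the 20-week endpoint. The documents do not establish that: the SAP is silent on unconfirmed progression there, and a later run of at least 133 days could still qualify. The 5.9-point change applies only to a subject whose status does change. The primary response-rate analysis, the sample size and the 80% power are unaffected. The SAP should be clarified, but the trial's main conclusion does not depend on it.

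**What to change.** In SAP 5.3.1 and Table 2, state that:

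- where Attachment 5 calls for a repeat assessment, progression is a DOR event only if the repeat confirms it, and is then dated at the first assessment;
- an unconfirmed progression is not a DOR event and does not break sustained response;
- if no repeat is done, or new cGVHD therapy starts before it, the first date counts as the event, so that a missing repeat does not work in the drug's favour;
- all unconfirmed progressions are listed.

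The SAP should also say which assessment serves as the repeat, since Attachment 5 does not fix its timing.

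Separately, protocol 8.1.3 and 10.2, which do not mention confirmation, should be reconciled with 9.1.3 and Attachment 5. Which of them governs stopping of treatment is for the sponsor to settle.

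The cost is a few sentences and a little more derivation work. The CRF must capture the repeat assessments. The Time and Events Schedule names no confirmatory visit, so it cannot be taken for granted that they are already collected, although 9.1.3 allows evaluations to be repeated more often when clinically indicated.

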## 2.10. Imputation Rules for Missing Dates

In general, imputation of missing dates will be made for AE onset date, AE resolution date, date of death, start and end dates of prior and concomitant and subsequent therapies, transplantation date, and date of initial diagnosis according to the following rules.

- If the date is completely missing, no imputation will be made.
- If the year is missing, then no imputation will be made.
- If only the year is present but the month and day are missing, then June 30th will be used.
- If only the day is missing but the year and month are available, then the 15th of the month will be used.

In addition, for date of initial diagnosis, the imputed date will be adjusted sequentially using the following steps:

- If only the day is missing;
  - if month and year of start of 1st line of prior therapy are the same year and month of diagnosis, and day of start date of 1st line of prior therapy is available, then the day of start date of 1st line of prior therapy will be used.
  - otherwise, the 15th of the month will be used.
- If both month and day are missing;
  - if year of diagnosis is the same as year of start of 1st line of prior therapy, and month info is available for start date of the 1st line of prior therapy, the month of start date of 1st line of prior therapy will be used.
    - if day of start date of 1st line of prior therapy is available, then the day of start date of 1st line of prior therapy will be used.
    - otherwise, the 15th of the month will be used.
  - otherwise, June 30th will be used.

- If the imputed date for initial diagnosis is on or after the first dose date, then first dose date -1 day will be used.

In addition, for date of prior and subsequent therapies, the imputed date will be adjusted sequentially using the following steps:

- If such imputed date for prior therapies is on or after the first dose date, then first dose date -1 day will be used.
- If such imputed date for subsequent therapies is before date of last dose, then date of last dose +1 day will be used.
- If prior or subsequent therapy start date is not missing and is after the imputed end date, then the start date will be used as the end date.

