**Table 4: Date of Event or Censoring for Failure Free Survival**

Situation	Date of FFS event or Censoring	Outcome
Death	Date of death	Event
New subsequent cGVHD treatment	Date of starting the new subsequent cGVHD treatment	Event
Relapse of malignancy	Start date of relapse of malignancy	Event
Not known to have event at the data analysis cutoff date (this includes subjects who were known to have event after the data analysis cutoff date)	Date of last known date (last visit) showing no evidence of event.	Censored

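### SAP 2.10 and SAP 5.3.1 give the same partly known start of subsequent cGVHD treatment two different dates, so duration of response can contradict responder status or censor a documented progression

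*SAP*

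**What the plan says.** SAP 2.10 sets the general rule for partial dates, and its scope includes "start and end dates of prior and concomitant and subsequent therapies".

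- Day unknown: "If only the day is missing but the year and month are available, then the 15" (the 15th of the known month).
- Month and day unknown: "If only the year is present but the month and day are missing, then June 30".
- Floor for later treatments: "If such imputed date for subsequent therapies is before date of last dose, then date of last dose +1 day will be used".

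SAP 5.3.1, in the text below Table 2, gives another rule for incomplete start dates of subsequent cGVHD treatment: "the partial date will be imputed as the earliest possible date that incorporates the available information from the partial date", provided that it "does not contradict last dose date of study drug". This sentence stands under Duration of Response only.

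SAP 5.1.2 settles which rule applies: "Unless specified otherwise, missing values will not be imputed and partial dates are described in Section 2.10". So 5.3.1 governs DOR and 2.10 governs the rest. The rest includes the no-new-therapy condition in the response definition (SAP 5.2.1) and the FFS event date in Table 4, "Date of starting the new subsequent cGVHD treatment". Sustained response has no date rule of its own and falls under 2.10 by default.

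**The concern.** DOR is calculated for responders only. Whether a subject is a responder depends on when new cGVHD treatment began, and so does the date at which DOR is censored. The SAP takes the first from 2.10 and the second from 5.3.1, so one real event can carry two dates. Two results then look wrong:

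- **(a)** A subject counts as a responder under the later date, while the earlier date censors DOR at an assessment before the response. The duration is negative, and the SAP does not say what to do with it.
- **(b)** Table 2 counts progression as an event only if it falls on or before the start of new treatment. The earlier date can move that start ahead of a documented progression, which is then censored. The later date would have kept it as an event.

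At stake are the coherence of DOR with the response and FFS results, and the DOR event count among a small number of responders (0.60 × 17 = about 10 at the planned rate).

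**Working it through.** **The plan's own figure.** With 17 subjects, the exact 95% lower limit exceeds 0.25 from 9 responders upward (9/17: 0.278; 8/17: 0.230). Power at a true rate of 60% is 0.801, so the stated figure of at least 80% is reproduced. The point made here does not rest on it.

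**The two rules.** Let L be the last dose date.

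- Date A (SAP 2.10): the 15th of the known month, or June 30; replaced by L + 1 day if before L.
- Date B (SAP 5.3.1): the 1st of the known month, or 1 January; not before L. This reads not contradicting last dose as on or after last dose.

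Largest gap, day missing: 15 − 1 = 14 days. Largest gap, month and day missing: 1 January to 30 June = 180 days (181 in a leap year). Over a grid of last-dose and start dates, the gaps ran from 0 to 14 and from 0 to 181 days, and both dates always fell on or after L.

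**When the gap matters.** Let x be the date of first response (case a) or of progression (case b). The rules give conflicting results only if B < x ≤ A. Because B is never before L, x must fall after last dose. A response or progression documented on or before last dose is never affected.

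**Case (a), day missing (invented dates).** First dose 1 April 2019; assessment 29 April, stable disease; last dose 11 May; first PR at the End-of-Treatment Visit on 10 June (11 May + 30 days); new treatment recorded as June 2019.

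- A = 15 June. The PR on 10 June precedes it, so the subject is a responder.
- B = 1 June. The last assessment on or before it is 29 April, so DOR = 29 April − 10 June = −42 days.

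**Case (a), year only.** Assessment 26 November 2018; last dose 10 December 2018; first PR 9 January 2019; new treatment recorded as 2019.

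- A = 30 June 2019: responder.
- B = 1 January 2019: DOR = 26 November − 9 January = −44 days.

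**Case (b).** Same dates as the first example, but PR on 29 April and progression documented on 10 June.

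- A = 15 June. Progression precedes it: DOR event at 10 June − 29 April = 42 days.
- B = 1 June. Treatment precedes progression: DOR censored at 29 April, 0 days.

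**With one date S throughout.** A responder needs a first response on or before S, and DOR is censored at the last assessment on or before S. That assessment cannot precede the response, so a negative DOR is impossible. In the first example, A throughout gives a responder with DOR censored at 0 days. B throughout gives no response at that assessment, and hence no DOR.

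**The case against.** The strongest reply is that this is a general rule with a stated exception. SAP 2.10 is introduced as general, 5.1.2 lets other sections depart from it, and 5.3.1 does so for DOR. That stands: there is no doubt about which rule applies where.

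A reader might go further and infer that the primary result is at risk, since one subject is 1/17 = 5.9 points and 9 of 17 passes while 8 of 17 does not. The documents do not support this. Responder status follows 2.10 alone, so the presence of 5.3.1 reclassifies nobody on the primary endpoint.

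The last-dose floor also removes most cases. Case (a) needs a first CR or PR after stopping ibrutinib, later cGVHD treatment with a partial start date, and a response between the two imputed dates. It is possible, because cGVHD is assessed at the End-of-Treatment Visit and at follow-up visits, and the response definition is not limited to time on drug. But it should be rare.

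Nor is the earliest date simply the safer one. Protocol 9.1.3 asks that the End-of-Treatment Visit come before any subsequent cGVHD treatment. If that was followed in the examples, the true start was after 10 June and date B is the wrong one. Extending the earliest-date rule unguarded to the primary endpoint could turn a true responder into a non-responder. Conversely, the mid-month date can admit a response recorded after treatment really began.

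What remains is that clear precedence does not make the two dates compatible. Case (b) does not need a late first response: it can arise in any responder who stops for another reason, progresses in follow-up and then starts new treatment on a partly known date.

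**Conclusion.** The point holds as an inconsistency across endpoints. Followed as written, the SAP can give a responder a negative DOR, and can censor a documented progression because of how a partial date was filled in. The discrepancy is at most 14 days with the day missing and about 180 days with month and day missing.

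The effect is mainly on DOR and FFS, both analysed descriptively; FFS is exploratory. No change in the primary result follows from it. The documents give no frequency of partial start dates, so the number of subjects affected cannot be estimated.

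The conclusion assumes that 5.3.1 allows an imputed start on the last dose date itself, and that an assessment on or before the imputed start counts as free of new treatment. The example dates are invented, with the End-of-Treatment Visit placed 30 days after last dose.

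**What to change.** Derive one start date of subsequent cGVHD treatment per subject and use it for response, sustained response, DOR and FFS. Make SAP 2.10 and SAP 5.3.1 both refer to it, and delete the separate sentence below Table 2. The imputed date should be:

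- compatible with the known part of the date;
- not before the last dose of study drug;
- not before any response or progression assessment documented as made before new treatment started.

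Within those limits, either the mid-month or the earliest date can serve as the starting value, provided it is the same for every endpoint. The third condition is essential: the earliest-date rule should not be carried to the primary endpoint without it. A single date removes case (a). The third condition removes case (b) wherever the order of assessment and treatment is documented.

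The cost is SAP wording and minor programming, with no new data. A few imputed dates will shift slightly.
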